### **6.3 Study Visit 3 (Day 2) - Treatment Period**

Subjects are not to take their morning dose of study drug at home as pre-dose assessments are performed at this Study Visit.

- 1. Vital signs pre-dose (BP after being seated for 5 minutes, pulse, respiratory rate and temperature)
- 2. Concomitant medications will be recorded
- 3. Adverse events will be recorded
- 4. 12-Lead ECG (x3) 2-3 minutes apart pre-dose and 1 hour post-dose
- 5. Laboratory studies (pre-dose) (non-fasting):
  - a. Quantitative PCR for HDV viral load

- b. Pre-dose and 1 hour post-dose blood samples (plasma and serum) for viral mutation analysis, resistance phenotyping, and analysis of drug mechanism and treatment response. These analyses include molecular and genetic analysis of drug mechanism, viral/host factors influencing treatment response (e.g. genotype and subgenotype analysis, quasispecies analysis, determination of drug and potential metabolite levels in plasma).
  - c. Blood sample for monitoring immunologic changes in peripheral blood mononuclear cells (PBMC).
6. Dosing Instructions:

Dosing with EBP-994 alone or in combination with Norvir® and/or Pegasys® should occur after the ECG has been performed and pre-dose lab samples drawn. The subject should receive morning dose of study drug(s). The post-dose ECG should be conducted one hour post-dose followed by the post-dose vitals and blood sampling.

The subject should bring the container(s) of study drug(s) dispensed at Study Visit 2 to this visit. Study personnel will assess dosing compliance and return container(s) to patient. No additional study drug will be dispensed at this visit. Subjects should be instructed to bring all container(s) and any unused study medication to the next study visit. Subjects should be instructed NOT to take their morning dose of study drug on the morning of the next Study Visit, Day 3, as pre-dose assessments will be conducted. Subjects should be sent home three hours post-dose.

#### **6.4 Study Visit 4 (Day 3) - Treatment Period**

Subjects are not to take their morning dose of study drug at home as pre-dose assessments are performed at this Study Visit.

1. Brief physical examination pre-dose (performed by a physician, nurse practitioner, physician's assistant or nurse). This includes weight as well as HEENT, heart, lungs, abdomen and lower extremity.
2. Vital signs
3. Concomitant medications will be recorded
4. Adverse events will be recorded
5. Laboratory studies (Pre-Dose) (non-fasting):
  - c. Serum chemistry panel, including liver function tests and albumin
  - d. Complete blood count (CBC with differential and platelet count)
  - e. Quantitative PCR for HDV viral load
  - f. Urinalysis

- g. Blood sample for monitoring immunologic changes in peripheral blood mononuclear cells (PBMC).
6. Dosing Instructions:  
Dosing with EBP-994 alone or in combination with Norvir® and/or Pegasys® should occur after the pre-dose vital signs have been taken, the physical examination performed, and pre-dose lab samples drawn. The subject should receive morning dose of study drug.

The subject should bring the container(s) of study drug(s) dispensed at Study Visit 1 to this visit. Study personnel will assess dosing compliance and return container(s) to patient. No additional study drug will be dispensed at this visit. Subjects should be instructed to return all container(s) and any unused study medication at the next study visit. At each subsequent Study Visit, drug accountability will be performed for each subject to ensure that the subject is compliant with dosing. Subjects should be instructed NOT to take their morning dose of study drug on the morning of the next Study Visit, Day 7, as pre-dose assessments will be conducted. Subjects should be sent home three hours post-dose.

## **6.5 Study Visit 5 (Day 7±2 days) - Treatment Period**

Subjects are not to take their morning dose of study drug at home as pre-dose assessments are performed at this visit.

1. Brief physical examination pre-dose (performed by a physician, nurse practitioner, physician's assistant or nurse). This includes weight as well as HEENT, heart, lungs, abdomen and lower extremity.
2. Vital signs pre-dose.
3. Concomitant medications will be recorded
4. Adverse events will be recorded
5. Laboratory studies (Pre-Dose) (non-fasting):
  - a. Serum chemistry panel, including liver function tests and albumin
  - b. Complete blood count (CBC with differential and platelet count)
  - c. Quantitative PCR for HDV viral load
  - d. Pre-dose and post-dose blood samples (plasma and serum) for viral mutation analysis, resistance phenotyping, and analysis of drug mechanism and treatment response
  - e. Urinalysis
  - f. Blood sample for monitoring immunologic changes in peripheral blood mononuclear cells (PBMC).

**6. Dosing Instructions**

Dosing with EBP-994 alone or in combination with Norvir® and/or Pegasys® should occur after the pre-dose vital signs have been taken, the physical examination performed, and pre-dose lab samples drawn. The subject should receive morning dose of study drug(s).

The subject should bring the container(s) of study drug(s) dispensed at Study Visit 1 to this visit. Study personnel will assess dosing compliance and return container(s) to patient. A new container of study drug will be dispensed at this visit. Subjects should be instructed to return all container(s) and any unused study medication at the next Study Visit. At each subsequent Study Visit, drug accountability will be performed for each subject to ensure that the subject is compliant with dosing. Subjects should be instructed NOT to take their morning dose of study drug on the morning of the next Study Visit, Day 14, as pre-dose assessments will be conducted. Subjects should be sent home three hours post-dose.

**6.6 *Study Visit 6 (Day 14±2days) - Treatment Period***

Subjects are not to take their morning dose of study drug at home as pre-dose assessments are conducted at this visit.

1. Brief physical examination pre-dose (performed by a physician, nurse practitioner, physician's assistant or nurse). This includes weight and vital signs as well as HEENT, heart, lungs, abdomen and lower extremity.
2. Vital signs pre-dose
3. Concomitant medications will be recorded
4. Adverse events will be recorded
5. Laboratory studies (Pre-Dose) (non-fasting):
  - a. Serum chemistry panel, including liver function tests and albumin
  - b. Complete blood count (CBC with differential and platelet count)
  - c. Quantitative PCR for HDV viral load
  - d. Pre-dose blood samples (plasma and serum) for viral mutation analysis, resistance phenotyping, and analysis of drug mechanism and treatment response
  - e. Urinalysis
  - f. Blood sample for monitoring immunologic changes in peripheral blood mononuclear cells (PBMC).
6. Dosing Instructions:

Dosing with EBP-994 alone or in combination with Norvir® and/or Pegasys® should occur after the pre-dose vital signs have been taken, the physical examination performed, and pre-dose lab samples drawn. The subject should receive morning dose of study drug(s). If there is not sufficient drug remaining the subject may take the capsules from the container dispensed at this study visit. EBP-994 and/or Norvir® should be taken orally with 240 mL of water.

The container(s) of study drug(s) along with any unused drug dispensed at Study Visit 4 should be returned at this visit. Study personnel will perform drug accountability on the returned container(s) of study drug(s). A new container(s) of drug will be dispensed at this visit. Subjects should be instructed to return all container(s) and any unused study medication at the next study visit. At each subsequent Study Visit, drug accountability will be performed for each subject and reviewed to ensure that subject is compliant with dosing. Subjects should be instructed NOT to take their morning dose of study drug on the morning of the next Study Visit, Day 28, as pre-dose assessments will be conducted. Subjects should be sent home 3 hours post-dose.

## **6.7 Study Visit 7 (Day 28±2days) - Treatment Period**

Subjects are not to take their morning dose of study drug at home as pre-dose assessments are conducted at this visit.

- 7 Brief physical examination pre-dose (performed by a physician, nurse practitioner, physician's assistant or nurse). This includes weight and vital signs as well as HEENT, heart, lungs, abdomen and lower extremity.
- 8 Vital signs pre-dose and after the post-dose ECG (BP after being seated for 5 minutes, pulse, respiratory rate and temperature)
- 9 Concomitant medications will be recorded
- 10 Adverse events will be recorded
- 11 12-Lead ECG (x3) 2-3 minutes apart pre-dose and 1 hour post-dose
- 12 Laboratory studies (Pre-Dose) (non-fasting):
  - f. Serum chemistry panel, including liver function tests and albumin
  - g. Complete blood count (CBC with differential and platelet count)
  - h. Quantitative PCR for HDV viral load
  - i. Pre-dose and post-dose blood samples (plasma and serum) for viral mutation analysis, resistance phenotyping, and analysis of drug mechanism and treatment response
  - j. Urinalysis

- k. Blood sample for monitoring immunologic changes in peripheral blood mononuclear cells (PBMC).
- 13 Pharmacokinetic blood samples (at the following time points: 0-pre-dose, post dose: 15 min, 30 min, 60 min, 90 min, 2 h, 2.5 h, 3 h, 4 h, ,6 h, 8, 10, 12 h) (for those subjects participating in the PK portion of this trial)

8 Dosing Instructions:

Dosing with EBP-994 EBP-994 alone or in combination with Norvir® and/or Pegasys® should occur after the pre-dose vital signs have been taken, the physical examination performed, the pre-dose ECG performed and pre-dose lab samples drawn. The subject should receive morning dose of study drug(s). If there is not sufficient drug remaining the subject may take the capsules from the container dispensed at this study visit. EBP994 alone or in combination with Norvir® should be taken orally with 240 mL of water. After dosing the post-dose procedures should be conducted in the following order: ECG (one hour post-dose), vital signs (post ECG), post-dose plasma and serum blood samples.

The container(s) of study drug(s) along with any unused drug dispensed at Study Visit 5 should be returned at this visit. Study personnel will perform drug accountability on the returned container(s) of study drug(s) to assess dosing compliance. A new container of drug will be dispensed at this visit to the subject. Subjects should be instructed to return all container(s) and any unused study medication at the next study visit. At each subsequent Study Visit, drug accountability will be performed for each subject to ensure that subject is compliant with dosing. Subjects should be instructed NOT to take their morning dose of study drug on the morning of the next Study Visit, Day 56, as pre-dose assessments will be conducted. Subjects should be sent home 3 hours post-dose, except for those participating in the PK component of the study.

If this is the last treatment visit, no new containers of drug(s) will be dispensed and all unused study medication will be collected.

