## 1.2 *Anticipated Risks To Subjects*

### Preclinical Safety Summary

Toxicokinetic data to support the toxicology program for the development of EBP-994 were obtained from three- and six-month toxicity studies in rats (19, 20), three-month and 12-month toxicity studies in cynomolgus monkeys (21, 22), and an embryo-fetal developmental toxicity and toxicokinetic study in rabbits (23). Additionally, a single-dose (SD) oral vs IV pharmacokinetic study in monkeys was conducted (24). Data on the distribution of EBP-994 are available from a single dose tissue distribution study in pigmented rats (25), a pilot whole body autoradiography (WBA) study in monkeys (26), and in vitro plasma protein binding studies (27, 28). The metabolism of EBP-994 was studied in vitro using liver microsomes, hepatocytes, and recombinant human cytochrome P450 (CYP) isozymes (29, 30, 31, 32). Additional information about the metabolism of EBP-994 was obtained from profiling in rats, monkeys, and humans (33, 34, 35, 36, 37, 38). The routes and extent of excretion of EBP-994 were evaluated in rats, monkeys, and humans (26, 33, 34, 35, 36, 37, 39, 40). The effects of EBP-994 on enzyme induction and enzyme inhibition were studied in vitro (41, 42) and in vivo (19, 21), and the potential for EBP-994 interactions related to transport proteins was also assessed (43, 44, 45).

Pharmacokinetic/toxicokinetic studies in rats, rabbits and monkeys given single and repeated oral doses of EBP-994 suggested slow absorption, with mean  $T_{max}$  = 2-8 hr. The compound had good bioavailability, with a mean absolute oral bioavailability of greater than 65% in rats and monkeys. In both species, increases in plasma AUC with increasing dose were observed but there were also cross-study and cross-species differences in exposure (e.g., sex-dependence) and accumulation patterns.

EBP-994 distributed rapidly into tissues, with liver, adrenal gland, pancreas, bile duct, and kidney reaching maximum concentrations of radioactivity by 4 hr post-dose; the tissue-to-plasma ratios of drug-derived radiocarbon in these tissues at 4 hr ranged from 3.90-14.7. Plasma protein binding to  $^3\text{H}$ -EBP-994 was  $\geq 99\%$  in all species over a 0.5-40.0  $\mu\text{g/mL}$  concentration range and binding to purified serum proteins (HSA, AAG, HSA-AAG) ranged from 94-98%.

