Inhibition of the hERG current by EBP-994 occurred at an IC50 of 1.3  $\mu$ M (representing an approximately 59-fold multiple over the mean free Cmax plasma concentration achieved at a clinical dose of 200 mg BID). This relatively large safety margin between the IC50 for SCH 66336 in the hERG assay and the free Cmax at a clinical dose of 200 mg BID, together with the absence of effects on isolated Purkinje fibers up to 1.1  $\mu$ M, is consistent with the absence of effects of EBP-994 on QT or QTc interval in vivo in anesthetized guinea pigs (total Cmax of 30  $\mu$ M) and in conscious monkeys (repeated-dose toxicity studies) administered EBP-994 for three-months and one year at doses up to 60 and 40 mg/kg, respectively. Metabolism studies conducted in vitro (30, 31, 32) and in vivo (rat, monkey, human) (33, 34, 35, 36, 37, 38) provided no evidence for the formation of human-specific EBP-994 metabolites. EBP-994 was shown to be extensively metabolized following SD administration of 14C-EBP-994 to rats (PO, IV), monkeys (PO, IV), and humans (PO) (33, 34, 36, 37); only small amounts of unchanged EBP-994 were detected in urine, bile or feces. LC-MS analyses indicated that the most common metabolic conversions involved oxidation (+O or +16) or dehydrogenation (-2H or -2) and were associated with changes in the pendant piperidine ring (33, 34, 36, 37).

Biliary and/or fecal excretion was the major route of elimination for administered drug and its metabolites following administration of 14C-EBP-994 to rats; urinary excretion (<1%) played a minor role (33, 39, 40). The available data likewise showed excretion patterns in monkeys and humans that were similar to those in rat.

Renal excretion in humans is not a major elimination pathway for EBP-994 and its metabolites. Mean urinary recovery of EBP-994 ranged from 0.001 to 0.5% of the dose over a 12-hr collection interval (46, 47, 48), and mean urinary radioactivity accounted for only ~0.7% of the dose following oral administration (37). After administration of 14C-EBP-994 to bile duct-cannulated rats, 16.5%-55.0% of the administered dose was collected in bile (up to 48-hr post-dose) of individual rats (33, 39). Evaluation of enterohepatic circulation by intraduodenal (ID) dosing of bile from 14C-EBP-994 PO-dosed donor rats to recipient rats suggested that <5% of the EBP-994 dose undergoes enterohepatic circulation (39).

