Dosing with EBP-994 alone or in combination with Norvir® and/or Pegasys® should occur after the pre-dose vital signs have been taken, the physical examination performed, the ECG performed and pre-dose lab samples drawn. EBP-994 capsules and/or Norvir® should be taken orally with 240 mL of water. After the morning dosing, the post-dose procedures should be conducted in the following order: ECG, vital signs, post-dose plasma and serum blood samples.

Subjects will be sent home 3 hours post-dose (except for those participating in the PK component of the study) with container(s) of study drug(s) and will be instructed to self-administer study drug(s) at appropriate intervals. Oral study drug should be swallowed with 240 mL of water. Subjects will also be given a diary to record the date, time and number of capsules they take.

Subjects should be instructed to bring all container(s) and any unused study medication to the study site at the next study visit. Subjects should be instructed NOT to take their morning dose of study drug on the morning of the next study visit, Day 2, as pre-dose assessments will be conducted.

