## **7.3 *Management Of Toxicity Related To Study Drug***

Safety will be monitored by assessing vital signs, adverse events, concomitant medications and laboratory and ECG results. ECGs will be conducted in triplicate and vital signs assessed at each Study Visit. During the treatment period, ECGs will be conducted pre and one hour post-dose. Vital signs will be taken pre-dose and following the post-dose ECG.

The most common side effects seen with lonafarnib (the active ingredient of EBP-994) are gastrointestinal (diarrhea, nausea, and vomiting).

There were no serious adverse events (SAEs) observed in the studies conducted in healthy volunteers. The SAEs reported in at least 2% of subjects in the Phase 1 and Phase 2 studies conducted in subjects with solid tumors or hematologic malignancies included fever (6%), diarrhea (6%), dehydration (6%), febrile neutropenia (4%) and sepsis (4%).

As with any anti-viral medication, a possible effect of EBP-994 is viral resistance. Hepatitis D viral load levels will be measured through quantitative PCR at all Study Visits. Viral mutation analysis and resistance phenotyping will be conducted to assess viral resistance to the study medication. The investigator may terminate the subject from the trial if, in his/her opinion, there is an unacceptable increase in HDV viral load. Moreover, the investigator is free to initiate licensed medications at any time point and decrease the dose of EBP-994 if deemed warranted for GI side effects.

During the conduct of the study, safety laboratory values will be assayed within 48 hours of the study visit and the Medical Monitor and Investigator will be informed within 24 hours of assay performance of laboratory abnormalities.

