#### **8.4.2 Clinical Laboratory and Vital Signs**

Clinical laboratory data (hematology, blood chemistry, and urinalysis) and vital signs will be summarized using descriptive statistics at baseline and each timepoint. Listings will display laboratory data at each period/timepoint collected by subject.

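### The only timed post-dose ECG is at 1 h, but the only Tmax in the documents (animal) is 2-8 h, so the QT check could precede peak exposure; no quantitative ECG/QTc summary is planned

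*Combined protocol and SAP*

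**What the plan says.** **ECG timing.** Sections 6.3 (Day 2) and 6.7 (Day 28) both specify "12-Lead ECG (x3) 2-3 minutes apart pre-dose and 1 hour post-dose". Section 7.3 generalises this: "During the treatment period, ECGs will be conducted pre and one hour post-dose". For Day 1, Section 6.2 gives a sequence without a clock time: "the post-dose procedures should be conducted in the following order: ECG, vital signs, post-dose plasma and serum blood samples". No later post-dose ECG is scheduled.

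**Absorption.** Section 1.2 states: "Pharmacokinetic/toxicokinetic studies in rats, rabbits and monkeys given single and repeated oral doses of EBP-994 suggested slow absorption", and gives a mean Tmax of 2-8 h. No human Tmax or half-life appears. Both are to be estimated in the optional PK subset (Sections 3 and 8.5).

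**Stay at the site.** On Day 2, "Subjects should be sent home three hours post-dose". Sections 6.2 and 6.7 set the same 3 h discharge, with PK participants staying longer.

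**Analysis.** Section 8.4.1 tabulates adverse events. Section 8.4.2 states: "Clinical laboratory data (hematology, blood chemistry, and urinalysis) and vital signs will be summarized using descriptive statistics at baseline and each timepoint". Neither names ECG or QTc. Section 8.2 assigns safety endpoints to the Safety Population without listing them. Yet ECG results are a named safety measure (Protocol Summary, Sections 3 and 7.3), and QT/QTc below 450 ms is an entry criterion.

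**The concern.** A pre-dose and post-dose ECG pair is informative about a concentration-related QT effect only if the second reading is taken near the highest exposure. The only absorption evidence in the protocol places the peak at 2 h or later, and no reason is given for choosing 1 h. If human absorption resembles the animal data, an absence of ECG change could partly reflect a reading taken on the rising limb.

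The analysis gap adds to this. Triplicate ECGs are collected, but no mean QTc, change from baseline or count above a threshold is planned. A drift in QTc that no investigator judged to be an adverse event would appear in no table. Few on-treatment ECGs are scheduled in Appendix A (Days 1, 2 and 28), so the timing and reporting of each one matter.

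**Working it through.** **1. The plan's own figure.** Section 1.2 gives a hERG IC50 of 1.3 µM, about 59 times the mean free Cmax at 200 mg BID.
- Total Cmax: 2.8 µg/mL ÷ 638.7 g/mol = 4.38 µM.
- Implied free Cmax: 1.3 ÷ 59 = 0.022 µM.
- Implied unbound fraction: 0.022 ÷ 4.38 = 0.5%, in line with the stated protein binding of at least 99%.

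The margin is internally coherent, and it is stated for 200 mg BID only.

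**2. How close to peak is 1 h?** The documents cannot answer this for humans, so the following is an illustration under assumptions.

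Inputs: Tmax 2, 4, 6 and 8 h (the animal range in Section 1.2, assumed to apply to humans); half-life 4-12 h (assumed); dosing interval 12 h (one of the intervals in Section 5.2).

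One-compartment model with first-order absorption, up to a constant:
- C(t) = ka/(ka − ke) × (e^(−ke·t) − e^(−ka·t)), with ke = ln 2 ÷ half-life.
- ka is solved from Tmax = ln(ka/ke)/(ka − ke). With absorption faster than elimination, Tmax of 6 or 8 h is feasible only for half-lives of 6 h or more.
- Repeated dosing: sum C(t + 12i) over earlier doses. The Day 2 morning dose is the third dose; Day 28 is taken as steady state.

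Example, Tmax 4 h and half-life 6 h: ke = 0.1155 and ka = 0.462.
- C(1) = 1.333 × (0.891 − 0.630) = 0.348.
- C(3) = 1.333 × (0.707 − 0.250) = 0.609.
- Cmax = C(4) = 1.333 × (0.630 − 0.1575) = 0.630.
- So after a first dose, 1 h is 55% of Cmax and 3 h is 97%.

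Concentration as % of Cmax, range over half-lives:

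| Tmax | First dose, 1 h | First dose, 3 h | Day 2, 1 h | Day 2, 3 h | Day 28, 1 h | Day 28, 3 h |
|---|---|---|---|---|---|---|
| 2 h | 85-90 | 94-97 | 90-96 | 92-95 | 90-97 | 92-95 |
| 4 h | 54-60 | 96-98 | 75-85 | about 100 | 76-89 | about 100 |
| 6 h | 39-42 | 83-85 | 80-82 | 98 | 82-88 | 98-99 |
| 8 h | 30-32 | 70-72 | 83 | about 96 | 87-89 | 98-99 |

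**3. The within-visit contrast.** The protocol pairs a pre-dose with a post-dose ECG, so the share of the pre-dose-to-peak rise also matters: (C(t) − C(0))/(Cmax − C(0)). At steady state with Tmax 4-8 h, 1 h captures 44-69% of the rise and 3 h captures 91-100%. With Tmax 2 h the two times are about equal (87-94% against 88-90%).

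**4. Downside of a later reading.** If human Tmax were 1 h, the 3 h level would be about 74-90% of Cmax.

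**5. Route of an ECG result into a table.** Section 7.1 defines an adverse event as any adverse change from baseline, and Section 8.4.1 tabulates those. No other route exists in Section 8.

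**The case against.** - **The Tmax is from animals.** This stands. A reader might infer that trial subjects are shown to be below peak at 1 h. The documents do not support that, because they give no human Tmax.
- **The low percentages belong to a first dose.** This stands. Levels of 30-60% of Cmax arise only after a first dose with Tmax of 4 h or more. They do not describe Day 2 or Day 28, the visits whose own sections fix 1 h, because earlier doses contribute. They bear on Day 1, where 1 h comes only from the general rule in Section 7.3.
- **Three hours is not better everywhere.** At Tmax 2 h the two times are equivalent on Days 2 and 28. The case for 3 h is that it loses almost nothing there and gains for longer Tmax.
- **The prior risk is low.** Section 1.2 reports no Purkinje-fibre effect up to 1.1 µM and no QT effect in guinea pigs or monkeys, and QT-prolonging drugs are excluded. This lowers the seriousness but does not replace a well-timed human reading. A reader might infer that 300 mg BID with Norvir erodes the hERG margin. The documents do not pair them: Norvir groups are capped at 150-200 mg daily. For 300 mg BID alone, dose-proportionality (assumed) would give 59 × 200 ÷ 300, about 39-fold.
- **ECG changes can still be tabulated.** Correct, as adverse events. To say that ECG findings would go unreported is too strong; what is missing is a quantitative summary.

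**Conclusion.** The concern holds in a limited form. The only timed post-dose ECG is earlier than the only Tmax in the documents, so the QT check could miss peak exposure, and Section 8.4 contains no quantitative ECG summary. If human Tmax lies in the animal range and a one-compartment model with a 4-12 h half-life is adequate, the shortfall at 1 h ranges from small to large after a first dose (30-90% of Cmax). It is modest on Days 2 and 28 (75-97%). Those repeated-dose figures assume a 12 h interval. Section 5.2 also allows 24 h dosing, where less carry-over would move them towards the first-dose figures, and 8 h dosing, where the reverse applies.

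This is a moderate point, worth acting on because a reading near 3 h is about equal or better across the cited Tmax range and needs no added ECG or visit. It does not show that a QT effect exists or that one would be missed.

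**What to change.** - **Timing.** In Sections 6.3, 6.7 and 7.3, take the existing post-dose triplicate ECG, with the vital signs that follow it, near the end of the 3 h stay. Start shortly before 3 h so that discharge is not delayed. State the same clock time in Section 6.2, which now gives only an order. If 1 h is kept, give the human data that justify it.
- **Blood samples.** Keep the Day 2 sample at 1 h unless its drug-level and mechanism analyses allow it to move. Edit the order-of-procedures text so that post-dose blood sampling does not shift unintentionally with the ECG.
- **Analysis.** In Section 8.4.2, add a descriptive summary of triplicate-mean QTc and its change from Day 1 pre-dose, at each ECG timepoint and by randomised group, with the number of subjects above the protocol's own 450 ms entry limit. Write the triplicate into Section 6.2, which lists a plain 12-lead ECG while the Appendix A footnote specifies three.
- **Reconcile the schedule.** The Protocol Summary and Sections 3 and 7.3 place ECGs at every visit. Appendix A lists them only at screening, Days 1, 2 and 28, and follow-up, and Section 6.10 refers back to Section 6.9, which has none.

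Cost: timing wording and one table, with no extra ECG or visit. The price is a reading somewhat past peak if human Tmax is near 1 h.
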